4.5 Exclusion criteria

•Known tomato allergy

- •Chronic medical conditions requiring active treatment (e.g. cardiovascular disease, diabetes, asthma)
- Gastro-intestinal disease/disorders
- Smokers
- Medically prescribed medication known to affect platelet function
- Self-prescribed medication known to affect platelet function (e.g. aspirin and non-steroidal anti-inflammatory drugs) unless participant is willing to give up.
- Bleeding disorders (e.g. haemophilia)
- Dietary supplements judged to affect study outcome
- Parallel participation in another research project which involves dietary intervention
- Blood donation within 16 weeks prior to the study
- Depressed or elevated blood pressure measurements (<90/50 or 95/50 if symptomatic or ≥ 160/100 mmHg)
- Any person related to or living with any member of the study team

4.6 Recruitment strategy

The study population will comprise apparently healthy men aged 18 - 26 years. A total of 99 participants are required to complete this trial. However, recruitment for this study will only cease once we are confident that the required number of participants will complete the study.

Recruitment of participants to this trial will be achieved through poster and E-mail advertisements (annex 7) placed across the University of Talca, inviting anyone who is interested in receiving information about the study to contact named researchers. Those expressing an interest will be provided with a participant information sheet (annex 8). If insufficient numbers of people are recruited from the University of Talca we may place advertisements in the local media.

After reading the information sheet, those interested in taking part will be invited to the research facility for an informal meeting with a member of the research team who will explain the study fully, focusing on the participant's involvement. Participants will be encouraged to ask questions at this stage prior to making any commitment. At the end of the meeting, participants will be given ample opportunity to consider whether they wish to take part in the study. If, following the consideration period they wish to participate in the study, they will be asked to contact a member of the research team to arrange an appointment at the research facility for the pre-study clinical screening.

4.7 Clinical screening

Clinical screening for this trial will be conducted as described in section 3.6. The only addition will be the assessment of platelet aggregation. This will be assessed by the research team and those participants not meeting the platelet aggregation response range defined in section 4.4 will be excluded from the trial.

4.8 Participant randomization

Participants in this parallel design study will ingest 1.0 or 2.5 g tomato pomace extract incorporated into a drink or a placebo control drink, over a 5 day period. Each treatment will be assigned a letter (A-C). Each time a participant is successfully recruited onto the study, he will be assigned the next allocated treatment. Randomization to treatment will be assigned by the computer programme randomization.com. The participants will be blinded to the treatments.

4.9 Preparation of tomato pomace drinks

The tomato pomace that will be used in phase 2 is that described in section 3.7. Immediately prior to ingestion, 'drinks' containing the appropriate mass of tomato pomace extract will be prepared at the research facility as follows:

Low dose pomace extract -1.0 g powder will be accurately weighed before dissolving in flavoured water to a final mass of 100 g High dose pomace extract -2.5 g powder will be accurately weighed before dissolving in flavoured water to a final mass of 100 g Placebo control -100 g flavoured water

Flavoured water is necessary to ensure that the participants are blinded to the test product consumed.

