Immediately prior to ingestion, 'drinks' containing the appropriate mass of tomato pomace extract will be prepared at the research facility as described below. The water used to dilute the extract will be flavoured using a commercially available orange flavoured powder (Kool aid) which will be diluted according to the manufacturer's instructions before adding to the tomato pomace extract. Flavoured water is necessary because this is how we intend to blind the participants to the test product in phase 2.

- 1) Low dose pomace extract 1 g extract will be accurately weighed before dissolving in flavoured water to a final mass of 100 g
- 2) Medium dose pomace extract 2.5 g extract will be accurately weighed before dissolving in flavoured water to a final mass of 100 g
- 3) High dose pomace extract 10 g extract will be accurately weighed before dissolving in flavoured water to a final mass of 100g

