3.10 Participant randomization

Participants in this ascending dose human tolerance study will ingest 1, 2.5 or 10 g tomato pomace incorporated into a drink, over a 5 day period. Each treatment will be assigned a letter (A-C). Once all 15 participants have been recruited they will be block randomized to treatment by the computer programme randomization.com. The participants will be blinded to the treatment dose.

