4.3 Study design

A single blind, parallel design (3-groups), placebo controlled trial will be conducted to assess the acute and longer term effects of ingesting a tomato pomace extract on platelet aggregation. Participants will be randomized to receive either: a) 1.0 g tomato pomace extract delivered in flavoured water b) 2.5 g tomato pomace extract delivered in flavoured water or c) Flavoured water (placebo control). A total of 99 people are required to complete (n=33/group). Each group will ingest either a treatment or placebo once daily, for 5-days. For 14-days preceding the baseline assessment day and for the 5-day period of intervention, participants will completely exclude from the diet some foods/beverages that are known to affect platelet function (tomato and all tomato based products, alcohol, cocoa and cocoa products and green tea). To assess the acute effects of the intervention on platelet aggregation, a blood sample will be obtained before ingestion (D15; 0-h) and post ingestion (D15; 3-h) of the treatment. To assess the longer term effects, further blood samples will be taken at the end of the intervention period (D19; 0 and 3-h). Figure 2 is a schematic overview of phase 2.

[figure not shown]

Figure 2. Schematic overview of phase 2

- 4.4 Inclusion criteria
- Apparently healthy men aged between 18 and 26 years
- BMI >19.5 and <26.0

• Platelet aggregation response corresponding to $\geq 65\%$

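### Participant blinding rests on flavouring alone: nothing in the placebo stands in for the extract, and the protocol text describes no masking of appearance and no check that the drinks match

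*Combined protocol and SAP*

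**What the plan says.** Section 4.3 declares the level of masking: "A single blind, parallel design (3-groups), placebo controlled trial will be conducted". Section 4.8 says who is masked: "The participants will be blinded to the treatments". Nobody else is named as blinded.

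The means of blinding is stated twice, and both times it is flavouring. Section 3.7, on the Phase 1 drinks, looks ahead: "Flavoured water is necessary because this is how we intend to blind the participants to the test product in phase 2". Section 4.9 repeats it for Phase 2: "Flavoured water is necessary to ensure that the participants are blinded to the test product consumed". The flavouring is a "commercially available orange flavoured powder (Kool aid") made up at the manufacturer's dilution.

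Section 4.9 then gives the recipes. The low and high dose drinks contain 1.0 g and 2.5 g of extract powder, each dissolved in flavoured water to a final mass of 100 g. The third drink is listed as "Placebo control -100 g flavoured water".

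**The concern.** Section 4.9 says that flavouring is there to ensure the blind. Flavouring can help to mask taste. The section does not address colour, cloudiness or texture, and the placebo contains no inert substitute for the extract. If the extract alters the drink in a way that a man can see, he may form a view of his allocation on D15, at the first dose.

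Participant blinding is the only masking that the plan claims. If it failed, two things would be open to influence:

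- **Behaviour between D15 and D19.** The men leave the facility each day under an exclusion of tomato, alcohol, cocoa and green tea, and must return on four further mornings. A man who believes he is on placebo might keep to the exclusion less well, or attend less reliably.
- **Adverse events.** Section 5.1 records events reported by the participant, and a belief about allocation can colour such reports.

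**Working it through.** The plan gives no figure for the quality of the blind, so there is none to reproduce. The check sets the relevant passages side by side.

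**1. What is matched.** From the recipes in section 4.9, extract content = extract mass / final mass:

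| Drink | Extract (g) | Flavoured base (g) | Extract by mass |
|---|---|---|---|
| Placebo | 0 | 100 | 0 / 100 = 0% |
| Low dose | 1.0 | 100 − 1.0 = 99.0 | 1.0 / 100 = 1.0% |
| High dose | 2.5 | 100 − 2.5 = 97.5 | 2.5 / 100 = 2.5% |

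The type of base and the total mass are matched. The extract has no counterpart in the placebo. The documents do not say whether 1.0% or 2.5% of extract can be seen, tasted or felt in the drink.

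**2. Whether appearance is masked.** Sections 3.7, 4.9 and 4.10 describe weighing, dissolving, fresh preparation each morning and drinking at the facility. None mentions the container, a lid or opacity.

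**3. Whether the match is checked beforehand.** Phase 1 does not do this. All of its drinks contain extract (1.0, 2.5 or 10 g), and its blind is between doses: "The participants will be blinded to the treatment dose". Its assessments (section 3.2) are blood pressure, pulse, gastro-intestinal well-being and blood tests. No extract drink is compared with plain flavoured water.

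**4. Whether the blind is checked afterwards.** The D15 and D19 questions (Annex 9) are described in section 4.10 as health related. Section 4.14 contains no summary of treatment guesses. The annexes are not in the text available to me, so the accurate statement is that the protocol text describes no test.

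**5. Which results are exposed.**

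- *Run-in, days 1–14.* Completed before the first drink, so not exposed.
- *Acute comparison, D15 0 h to 3 h.* The men eat freely only after the assessment period, so the diet route does not reach it.
- *D19 samples.* Four intervals away from the facility lie between the first drink and D19 (D15–16, D16–17, D17–18, D18–19). Lapses in diet, or missed visits, that differ by group could affect these samples. Section 4.11 covers only drinking the treatment, and no diet record is described, so such lapses would probably go unseen.
- *Direct expectation effect on the endpoint.* Section 4.13 reads percent maximal amplitude by light transmission on a Lumi-aggregometer, so a participant's belief has little direct route to it.

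**The case against.** The strongest reply is that there is no evidence of a mismatch. The flavoured water is itself made from an orange flavoured powder, and nothing says that it is colourless. Section 3.7 describes a pomace that is extracted and dried, and both preparation sections have the extract dissolved, which does not suggest visible residue. In a parallel trial each man receives one drink and has no second drink of his own to judge it against. All of this stands. A reader might infer that the placebo lacks powder and colour, or that participants will be unblinded; the documents support neither inference.

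The plan also works against the behavioural route. Section 4.12 pays 5,000 pesos for keeping to the dietary restrictions and 2,500 pesos per study blood sample. Section 4.10 repeats the dietary instruction on days 16–18. Dosing is supervised. These points reduce the risk. They do not remove it, because payment and instruction are not measurement.

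A reader might also want to express the concern as lost power. That needs a rate of dietary lapse in each group and an effect per lapse. The documents give neither, so any such figure would rest on invented inputs. If placebo men did lapse towards foods with anti-platelet activity, placebo aggregation would fall and the D19 contrast would shrink. That particular pattern would not create a false benefit.

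**Conclusion.** The point holds as a gap between what section 4.9 claims and what it provides. Flavouring is the only stated means of the only stated blind, nothing in the placebo stands in for 1.0 or 2.5 g of extract per 100 g, and neither masking of appearance nor a check of the match is described. It does not show that the blind will fail.

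The size cannot be quantified, because the documents contain no sensory data and no adherence data. The exposure is confined to diet adherence and attendance between D15 and D19, hence the D19 comparison, and to self-reported adverse events. The acute D15 comparison is not exposed through diet. The conclusion assumes that the annexes, which I could not see, contain no masking instruction or blinding check. This is an inexpensive improvement to make before the trial starts, not a threat to its validity.

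**What to change.** In section 4.9, state that all three drinks are served in identical opaque lidded cups with a straw, closed before they are handed to the participant.

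The cost is disposable cups. The product, the doses, the sample size and the visit schedule do not change. The limit should be stated: cups hide appearance only, and leave taste and mouthfeel as they are.

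Optionally, add to section 4.10 one question after the 3-h sample on D19 asking which treatment the man thinks he had (active, placebo or don't know), and report the answers by group. Asked after the last sample, it cannot affect the outcome. It would be descriptive only: it cannot restore the blind, and it does not measure diet.

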4.10 Intervention procedure

The test arm will comprise a 5 day intervention period which will be preceded by a run-in phase of 14 days. For standardisation purposes all trial procedures between days 15 - 19 will be conducted in the morning time following an overnight fast. A test arm is described below.

Days 1-14 – During the 14-day 'run-in' period, participants will be instructed to avoid foods and beverages known to significantly contribute to anti-platelet activity. A 14-day period is thought to be sufficient as this comprises the average lifespan of platelets (~ 10 days) and allows for equilibration to dietary change. The foods and beverages to be avoided include tomato and all tomato based products, alcohol, cocoa and cocoa based products and green tea. In the event that a participant self-prescribes medication for minor illness during this time period, he will be instructed to contact a member of the research team who will assess the impact of the medication on platelet function and decide whether or not the run-in period should be rescheduled.

Day 15 – Participants will arrive at the research facility on the morning of day 15 having fasted from 10 pm the night before. Prior to conducting any clinical procedures the participant will be asked some basic health related questions (Annex 9) to establish whether or not any changes in medical conditions/medications etc. have occurred since their last visit and that they are well enough to proceed with the study day assessment. A baseline (t=0h) fasted blood sample (15 mL) will be collected by venepuncture. Once collected, participants will ingest the allocated treatment drink. A further blood sample will be obtained 3-h post ingestion (15 mL) to assess the acute effects of tomato pomace ingestion on platelet aggregation. At the end of the assessment period participants will be free to eat and drink ad libitum.

Days 16 – 18 - Participants will return to the research facility each morning having fasted from 10 pm the night before. The allocated treatment will be prepared fresh each morning by a member of the research team and ingested by the participant whilst in the research facility. On departure, the participants will be instructed to continue avoiding the foods and beverages known to significantly contribute to platelet activity.

Day 19 – Participants will return to the research facility on the morning of day 19 having fasted from 10 pm the night before. Prior to conducting any clinical procedures the participant will again be asked some basic health related questions (Annex 9) for the reasons already described. A blood sample (15 mL) will be collected by venepuncture. The participant will once again ingest the allocated

treatment drink and a further fasted blood sample (15 mL) collected 3-h later. This completes participation in the trial.

In the unlikely event that a participant is unable to attend the pre-scheduled assessment days (e.g. minor illness) they will be given the opportunity to repeat the treatment at a later date. The total blood volume collected from each participant is 85 ml (incl. screening sample).

4.11 Treatment compliance

Each participant will ingest the allocated treatment at the research facility.

4.12 Participant payments

Each participant will receive an inconvenience allowance of 15,000 Chilean Peso upon completion of the study or pro-rata for non-completion. The inconvenience payment has been calculated as follows: 2500 Chilean Peso per study blood sample (x4 samples=10,000) and 5,000 Chilean Peso for compliance with dietary restrictions.

4.13 Assessment of platelet function

Whole blood will be collected by venepuncture directly into 3.2% sodium citrate tubes (9:1 v/v) after discarding the first 2.0mL of the draw. Tubes will be centrifuged at 240 x g for 10 mins to obtain platelet-rich plasma (PRP). After aliquoting a portion of the PRP for platelet count (hematologic counter) the tubes will be further centrifuged at 650 x g for 10 mins to obtain platelet-poor plasma (PPP). The PRP will be adjusted to 200 x 10^9 platelets/ L with the PPP.

Aliquots of the adjusted PRP (480 μ L) will be pre-incubated (37^oC; 3 min) before the addition of the platelet agonists ADP (final conc. 2 and 4 μ mol/L) and collagen (final conc. 0.5 and 1 μ g/mL). Platelet aggregation will be measured by light transmission according to Born and Cross using a Lumi-aggregometer. The result of platelet aggregation (% maximal amplitude) will be determined using the software AGGRO/LINK.

4.14 Power calculations & statistical analysis

The primary outcome measure for this study is platelet aggregation. The sample size has been powered on data from a previous study reported by O'Kennedy et al [13], which is a study not too dissimilar to this one. In this trial, the effect size in platelet response between treatment (18 g tomato extract syrup) and control after stimulation of platelets with collagen was 17.4% with a standard deviation of 19.5%. Assuming a similar maximum difference between the control and the 2.5 g dose of tomato pomace extract, and half this difference for the 1.0 g dose of tomato pomace extract then to gain sufficient evidence to reject the null hypothesis of no differences between the 3 groups at the 5% significance level with 90% power would require 33 participants per group to complete the trial. The data will be analysed using one-way between subjects analysis of variance or its non-parametric equivalent (Kruskal–Wallis test by ranks). Post hoc comparisons between groups will use Tukey's honest significant difference (HSD) multiple comparison procedure.

5. Ethical considerations (Phases 1 and 2)

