4.1 Study hypothesis

Daily ingestion of a tomato pomace extract for 5 days will significantly reduce platelet aggregation in humans compared with a placebo control and in a dose dependent manner.

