4.2 Study Objectives

- 1) To determine the acute effect of ingesting two different doses of a tomato pomace extract on platelet aggregation
- 2) To determine the longer term effect of ingesting two different doses of a tomato pomace extract on platelet aggregation

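### The primary outcome is named only as platelet aggregation, with no agonist, concentration or time point, so the 5% level and 90% power belong to one test that the plan does not identify.

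*Combined protocol and SAP*

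**What the plan says.** - **Primary outcome (4.14):** "The primary outcome measure for this study is platelet aggregation". The sentence gives no agonist, concentration, day, hour or analysed quantity.
- **Assay (4.13):** aggregation is measured with ADP at 2 and 4 µmol/L and collagen at 0.5 and 1 µg/mL, four conditions in all.
- **Sampling (4.3):** for the acute effect, "a blood sample will be obtained before ingestion (D15; 0-h) and post ingestion (D15; 3-h) of the treatment". For the longer-term effect there are two more samples on D19, at 0-h and 3-h.
- **Objectives (4.2):** the first is "To determine the acute effect of ingesting two different doses of a tomato pomace extract on platelet aggregation". The second is the longer-term counterpart. Neither is marked as primary, and the opening summary also names both.
- **Hypothesis (4.1):** "Daily ingestion of a tomato pomace extract for 5 days will significantly reduce platelet aggregation in humans", compared with placebo and in a dose-dependent way.
- **Sample size (4.14):** a collagen result from an earlier study (difference 17.4%, SD 19.5%), half that difference for the 1.0 g dose, three groups, 5% level, 90% power, 33 completers per group. No collagen concentration or sampling time is given.
- **Analysis (4.14):** one-way ANOVA or Kruskal–Wallis, with Tukey's HSD for comparisons between groups. No rule says when Kruskal–Wallis replaces ANOVA.
- **Entry criterion (4.4):** "Platelet aggregation response corresponding to" at least 65%, again with no agonist named.

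**The concern.** A significance level and a power figure describe a defined test. Here the outcome is defined loosely enough that several tests fit it. Tukey's procedure controls error across the three groups within one test. It does nothing across agonists, concentrations or time points.

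Nothing in the plan prevents the concentration, hour or agonist from being chosen after the results are seen and that test then being reported as the primary outcome. A claim made that way would not carry the stated 5% error.

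The choice of D19 hour is also a choice of question. The 0-h sample follows four doses. The 3-h sample follows all five, but it also contains the acute effect of the fifth.

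The analysed quantity is open too. The plan does not say whether the post-baseline value, its change from D15 0-h or a baseline-adjusted value is compared.

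**Working it through.** **1. The plan's own figure.** Inputs from 4.14: means 0, 8.7 and 17.4 (as differences from control), SD 19.5, n = 33 per group, α = 0.05.

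Non-centrality λ = n·Σ(μᵢ − μ̄)²/SD² = 33 × (8.7² + 0 + 8.7²)/19.5² = 33 × 151.38/380.25 = 13.14, on 2 and 96 df. The non-central F distribution gives 90.2% power; n = 32 gives 89.2%. The stated 33 per group is therefore correct for one three-group ANOVA at 5%.

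**2. How many tests fit the text.**

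- Broadest reading: 4 conditions × 2 objectives = 8, or 4 conditions × 3 post-baseline samples = 12.
- Collagen on D19, taking the agonist from the sample-size text and the day from the five-day hypothesis: 2 concentrations × 2 hours = 4.
- One collagen concentration only, over two or three samples: 2–3.

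**3. False-positive rate if each test ran at 5% and any one counted.** With independent tests the rate is 1 − 0.95^m. Independence is implausible here: the four conditions are "Aliquots of the adjusted PRP" from one sample, and the samples come from the same men. The documents give no correlation, so a range is assumed. Correlated rates come from simulated null ANOVAs (3 × 33, 40,000 runs per cell). Two structures were used: equal correlation between all tests, and a condition-by-time product structure. Where two figures appear, they are in that order.

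| Assumed correlation | m = 2 | m = 3 | m = 4 | m = 8 | m = 12 |
|---|---|---|---|---|---|
| 0 | 9.8% | 14.3% | 18.5% | 33.7% | 46.0% |
| 0.5 | 9.3% | 12.6% | 15.8 / 16.3% | 25.4 / 27.9% | 33.0 / 36.4% |
| 0.9 | 7.3% | 8.5% | 9.7 / 10.1% | 12.5 / 13.1% | 14.1 / 15.7% |
| 0.95 | 6.6% | 7.7% | 8.2 / 8.7% | 9.9 / 10.5% | 11.0 / 12.1% |
| 0.99 | 5.6% | 6.0% | 6.4 / 6.4% | 7.2 / 7.1% | 7.4 / 7.5% |

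**4. If all tests were kept as co-equal.** Splitting 5% by Bonferroni at 33 per group gives power per test of 77.0% (4 tests), 69.0% (8) and 64.0% (12). Restoring 90% would need 44, 49 or 52 per group. This assumes that the planning effect and SD apply to every test.

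**5. Why the analysed measure matters.** Assume 19.5 is the SD of both the D15 0-h and the D19 value, with correlation r between them. The effective SD is 19.5·√(1 − r²) for baseline adjustment by ANCOVA (95 error df) and 19.5·√(2(1 − r)) for a change score.

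| r | 0 | 0.3 | 0.5 | 0.7 |
|---|---|---|---|---|
| ANCOVA power | 90.2% | 92.8% | 96.6% | 99.6% |
| Change-score power | 61.1% | 77.5% | 90.2% | 98.9% |

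The change-score row depends on that SD assumption. With an assumed baseline SD of 10, the change-score SD is √(100 + 19.5² − 2·r·10·19.5), and power is 82, 92, 97 and 99%. If 19.5 were itself the SD of a change, power would be 90.2% at every r.

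**The case against.** The strongest reply is that the plan is less open than a count of 8 to 12 suggests. The sample size rests on collagen, and 4.14 states a single null hypothesis across the three groups. No section says that each combination of condition and time is a separate test of the primary outcome. The hypothesis concerns five days of ingestion, and only the D19 3-h sample follows all five doses. On that reading two tests remain, differing only in collagen concentration, with a rate of about 7–10% for correlations of 0.9 down to 0.

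It can also be said that the error rates rest on an any-one-counts rule that the plan does not state and on correlations it does not give. The change-score figures likewise rest on a reading of 19.5% that the plan does not confirm.

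Much of this is fair, and it limits how the figures may be used. Collagen on D19 is the reading that the text favours, and the rates are conditional. But the collagen sentence reports an earlier study's result; it does not declare this trial's primary agonist. Section 4.3 assigns both D19 hours to the longer-term effect, so the five-day wording is a lean and not a choice. No section selects a concentration, a D19 hour or an analysed measure. The any-one-counts rule is neither stated nor excluded. The gap remains on every reading.

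**Conclusion.** The concern holds, and it should be settled before Phase 2 begins. The sample-size arithmetic is correct, but it covers one test that the plan does not name.

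The size of the error inflation cannot be fixed from the documents. If any one unadjusted test counted and there was no true effect, correlations of 0.9 down to 0 would give 7–14% with one collagen concentration, 10–19% for collagen on D19, and 12–46% on the broadest reading. The upper ends need independence, which is implausible. The lower ends are not floors, since the rate falls towards 5% as correlation nears 1.

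The conclusion does not depend on these rates: a primary test that can be picked after the data are seen does not carry the stated level. A choice made after the results are known cannot credibly repair this.

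**What to change.** Before the first Phase 2 sample, amend 4.14 to name one primary test. For example: collagen-induced aggregation at one stated concentration (0.5 or 1 µg/mL), at one stated D19 sample (0-h or 3-h, with a one-line reason), adjusted by ANCOVA for the D15 0-h value at the same concentration, compared across the three groups at 5%, with Tukey-adjusted comparisons of the group means. Another single, fully stated measure would also serve.

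Alongside this:

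- Make Kruskal–Wallis a sensitivity analysis, or state in advance when it replaces the primary test.
- Label all other conditions and time points as secondary, including the D15 3-h acute test, and either adjust them by Holm's method or report them descriptively. Testing the acute objective only after a significant primary result is optional.
- Mark in 4.2 which objective the primary test serves.

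The cost is wording in 4.14 and 4.2, plus the ethics committee approval that 5.7 requires before implementation. No extra participants, samples or assays are needed, because the D15 0-h sample is already planned. Power with ANCOVA stays at about 90% or more if 19.5% is the SD of the D19 value. The real price is that a positive result only on ADP, at the other collagen concentration or at another time point, including the acute effect, could no longer be claimed as primary.

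### Section 4.14 follows Kruskal-Wallis with a means-based procedure (Tukey HSD) and names no ordered test for the dose-dependence part of the 4.1 hypothesis

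*Combined protocol and SAP*

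**What the plan says.** **Hypothesis (4.1).** Daily intake for five days "will significantly reduce platelet aggregation in humans compared with a placebo control and in a dose dependent manner". The claim has two parts: a reduction against placebo, and an ordering by dose.

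**Objectives (4.2).** The acute and the longer-term effect of two doses. Neither objective asks for a dose-response test.

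**Design (4.3).** "A single blind, parallel design (3-groups), placebo controlled trial", with placebo, 1.0 g and 2.5 g, and 33 completers per group.

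**Sample size (4.14).** A difference of 17.4 with SD 19.5 is assumed for 2.5 g against control, "and half this difference for the 1.0 g dose of tomato pomace extract". The trial is sized for 90% power at 5% against the null of no difference among the three groups.

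**Analysis (4.14).** "one-way between subjects analysis of variance or its non-parametric equivalent", the alternative being Kruskal-Wallis. Pairs are then compared by Tukey's "honest significant difference (HSD) multiple comparison procedure". No other follow-up is named for either branch. No trend contrast, ordered rank test or dose regression appears, and no rule says which result would support dose dependence.

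**Measurements (4.3, 4.13).** Plasma is warmed "before the addition of the platelet agonists ADP" at two concentrations, or collagen at two concentrations. Samples are taken on day 15 at 0 and 3 h, and "further blood samples will be taken at the end of the intervention period (D19; 0 and 3-h". Section 4.14 does not say which agonist condition and time point decides the hypothesis.

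**The concern.** There are two gaps.

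**Rank branch.** Kruskal-Wallis would be chosen because the data look unsuitable for ANOVA. Tukey HSD then brings back the comparison of means and the pooled error variance that were just set aside. On skewed or heavy-tailed data the follow-up can lose power, or fail to find any differing pair after a significant overall test.

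**Dose dependence.** The sample size assumes an ordered pattern, but neither overall test uses the order. At least three readings of dose dependence stay open once results are known: both doses differ from placebo, 2.5 g differs from 1.0 g, or the group means merely fall in order. Their chances of success differ widely, and the plan does not choose among them. The choice can be repeated over several agonist conditions and time points.

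**Working it through.** **Inputs.** Means 0 / 8.7 / 17.4 (reductions; 8.7 is half of 17.4), common SD 19.5, n = 33 per group, 5% level: all from 4.14. Error df = 99 − 3 = 96.

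**1. The plan's own figure.** λ = n·Σ(μᵢ − μ̄)²/σ² = 33 × (8.7² + 0 + 8.7²)/19.5² = 33 × 151.38/380.25 = 13.14. Noncentral F with 2 and 96 df gives power 90.2% (89.2% at n = 32). The stated 33 per group for 90% is reproduced.

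**2. Tukey pairs.** SE of a difference = 19.5 × √(2/33) = 4.801. Critical |t| = q(0.95; 3, 96)/√2 = 2.381. Power from the noncentral t:

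| Pair | Difference | Noncentrality | Power |
|---|---|---|---|
| 2.5 g vs placebo | 17.4 | 3.62 | 89.1% |
| 2.5 g vs 1.0 g | 8.7 | 1.81 | 29.0% |
| 1.0 g vs placebo | 8.7 | 1.81 | 29.0% |

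Both adjacent steps are significant together in about 3% of simulated trials. Over an assumed SD range, the 2.5 g vs 1.0 g power is 49.3% at SD 15 and 18.7% at SD 24.

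**3. What an ordered contrast would do.** Centring the doses 0, 1.0, 2.5 gives coefficients −1.167, −0.167, 1.333.
- Contrast = −0.167 × 8.7 + 1.333 × 17.4 = 21.75 (unrounded coefficients). SE = 19.5 × √(3.167/33) = 6.041. Noncentrality = 3.60.
- Power is 94.6% alone, and 89.8% if run only after a significant F (400,000 simulated trials, normal data).
- Correlation with the 2.5 g vs placebo contrast = 2.5/√(3.167 × 2) = 0.993. The gated trend is significant without that Tukey pair in only 1.4% of trials.
- Gated power is 95.3% if only 2.5 g works (0/0/17.4) and 90.5% for a plateau (0/17.4/17.4), so the contrast does not identify the shape. For 0/17.4/8.7 the contrast alone has 29.7%, against 90.2% for F.
- Under the global null, F or an ungated trend rejects in 7.4% of trials. The gated trend rejects in 2.5%, all inside the F test's 5%.

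**4. Rank branch, normal data.** Kruskal-Wallis 88.4%. Jonckheere-Terpstra 93.8% alone, 88.0% gated. Dunn-Bonferroni 85.9% for 2.5 g vs placebo and 22.5% for each 1.0 g pair. Steel-Dwass about 26% for each 1.0 g pair.

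**5. Rank branch, non-normal data.** The documents give no distribution, so the shapes are assumptions: t with 3 df, and lognormal with log-scale SD 1, both scaled to SD 19.5 with the plan's shifts.

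| Shape | 2.5 g vs placebo, Tukey | 2.5 g vs placebo, Dunn | Kruskal-Wallis significant, no Tukey pair significant |
|---|---|---|---|
| t, 3 df | 90% | 99% | about 8% |
| lognormal | 88% | about 100% | about 11% |

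**6. Number of analyses (assumption, since 4.14 is silent).** Four agonist conditions × three samples after the first drink = up to 12. At a 2.5% null rate for each gated trend, independent analyses would give 1 − 0.975¹² = 26% chance of at least one false trend. Correlation among real analyses makes this an upper illustration.

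**The case against.** The strongest reply is that the trial was never sized for 2.5 g against 1.0 g, and low power for one post hoc pair is not an error. That stands. A reader might infer from the 29% that the sample size is wrong. It is not: 4.14 powers the three-group null, and that figure reproduces. A reader might also call 2.5 g vs 1.0 g the only planned comparison bearing on dose order. That goes too far: placebo is dose zero, so 1.0 g vs placebo bears on a monotone order as well. It is the only direct dose-to-dose comparison.

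Second, the added trend test nearly duplicates a pair already planned. This also stands. Under the plan's own means, about 36% of simulated trials have a significant gated trend with neither 1.0 g pair significant. Such a result rests on 2.5 g vs placebo, so the wording must limit what it can show.

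Third, a trend test on every agonist condition and time point would leave open which one decides 4.1. That is right, and the remedy has to name one.

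Fourth, ANOVA with Tukey serves the 4.2 objectives, and dose dependence is only a closing phrase in 4.1. True, but it is part of the sole stated hypothesis and has no decision rule.

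Fifth, the Kruskal-Wallis mismatch matters only if that branch is used. Agreed, yet the plan offers the branch and gives it an unsuitable follow-up.

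**Conclusion.** The point holds and is minor. In the rank branch the named follow-up tests means where the main test uses ranks. Under the assumed non-normal shapes this lowers power for 2.5 g vs placebo by roughly 9 to 12 percentage points relative to Dunn, and leaves a significant overall test with no significant pair in 8–11% of trials. On normal data the loss does not arise: Tukey is slightly more powerful than Dunn.

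Separately, the dose-dependence part of 4.1 has no ordered test and no decision rule. The one direct dose-to-dose comparison has 29% power, as has 1.0 g vs placebo. The benefit of adding a trend test is a rule fixed in advance, not new power.

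All power figures take 17.4 and 19.5 to apply to the analysed variable in this parallel design, as the protocol does. Their source is listed in the references as a crossover study. The SD range and the non-normal shapes are assumptions.

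**What to change.** Keep the ANOVA, the Tukey comparisons in the ANOVA branch, and the sample size. Add to 4.14:

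1. If Kruskal-Wallis is used, pairs will be compared with an adjusted rank-based procedure (e.g. Steel-Dwass or Dunn) instead of Tukey HSD.
2. Dose dependence will be tested with a linear contrast on dose (0, 1.0, 2.5 g), or with Jonckheere-Terpstra in the rank branch, at two-sided 5% and only if the overall test is significant. The 4.1 conclusion rests on one agonist condition and time point named before unblinding; trend tests elsewhere are exploratory.
3. A significant trend supports an overall trend across dose only. It does not show that 1.0 g works or that 2.5 g exceeds 1.0 g.

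Because only participants are described as blinded, item 2 should be settled before anyone compares aggregation results by group.

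**Cost.** Wording, and one more gated test per analysis; the same 99 men. The trend test adds little beyond 2.5 g vs placebo, cannot separate graded from threshold or plateau shapes, is weak for a non-monotone shape, and leaves the 29% unchanged. On normal data Dunn gives up some power against Tukey (about 22% vs 29% for each 1.0 g pair, 85.9% vs 89.1% for 2.5 g vs placebo), and it supplies no simultaneous intervals for differences.
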